Title: Innovative Teaching Solutions to Improve the Outcomes of Home Caregivers

V1.01.2023

PI00868

Abstract

Justification. Caring multipathological and polymedicated patients at homes is inexorably growing in OCDE countries, with a greater risk of suffering diverse errors made by their carers. **Objective.** To promote the training of home caregivers using five different educational solutions compared against the natural intervention. **Method.** Prospective, parallel and mixed research study with two phases. *Candidates:* will be home-based caregivers caring either a person with multiple co-morbid conditions or polymedication or a person that have a permanent device implanted such as a Port-a-Cath. *First phase:* Expert groups joined together to design and plan potential educational solutions directed to caregivers based on the identification of medication and home care errors, their causes and consequences and risk factors that favor them. *Second phase:* Inter- and intrasubject single-factor experimental design (6 groups, 5 experimental groups and control, with pre-post- intervention and follow up measures), simple random assignment, to determine the effectiveness several educational solutions (n=420 participants). The study will be carried out in primary care centers and caregivers' associations in Valencian Community, Andalusia, Madrid, Murcia and Catalonia. **Expected results.** To identify critical elements for risk management in the home for caregivers. To find the most effective and optimal educational solution that also reduces the impact of gender bias in this activity.

ClinicalTrial xxxxxxxxx

Overview and aim

The increase in the number of people with chronic diseases is a significant burden of care and consumption of health care resources all over the world. Most are elderly and, in some degree, dependent for their daily activities of a caregiver. Thanks to the work of people caring people at home, these people survive while preserving their well-being as much as possible. This work covers a range of activities from physical and emotional support for the promotion of autonomy to the management of their pharmacological treatment, in many cases applying more complex care. The sex bias generally prompts that the provision of care for dependent persons is carried out by women, which widens the already existing gender gap to the detriment of women.

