The project seeks to put people at the center of interventions while respecting their digital rights. The comparison between 360V, VR, RA, web-based information, written information and standard procedure, to determine which is the best way to train home caregivers in order to increase their technical competences and soft skills, including self-confidence, is the outcome this project would analyze. This study aims to explore the

experience and needs of caregivers (skilled and unskilled) of dependent and chronically ill patients and then to design and test the effectiveness of several interventions aimed at promoting safer medication use in the home.

Methods

Intervention design

This is a prospective, parallel, fully randomized (with simple random assignment of participants to one of six arms) experimental study to compare (inter-group and intra-subject PRE and POST measures) educational interventions aimed at training caregivers using typical scenarios during their work at home in order to reduce medication and caring errors and improve caregivers' motivations and self-efficacy.

Present protocol underwent the revision and approval of an Ethics Committee Board, obtaining the approval in December 2021 and January 2023 (CODES 21/063; 22/079 and 22/080). ClinicalTrial xxxxxxxx

Recruitment

Recruitment will be carried out in the collaborating centers through the programmes for complex chronic patients, schools for carers, and associations and foundations for carers and/or diseases causing dependency situations using the "snowball" technique.

Participants (caregivers) will be recruited during a regular consultation where they go to accompany the person they care for to the consultation, or in a clinical consultation of their own where they can comment that they are caring for a person at home. Recruitment will be carried out through systematic sampling according to the list of people seen in the consultation, using $k=3$. The collaborator will systematically select 1 out of every 3 patients cited in the consultation list. If the person refuses to be included in the study, the next person on the list will be invited and then $k=3$ will be applied.

Additionally, in the recruitment of caregivers, two aspects must be considered:

- Qualification of the caregivers

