- *Arm 2-Experimental group 2:* Intervention with written materials and demonstration videos specifically designed for this study. **This arm will evaluate the effect of a traditional, more passive form of learning, with little degree of interaction with the content.**
- *Arm 3-Experimental group 3:* Psychoeducational intervention specifically designed for this study. **With this specific intervention, participants will learn by sharing information with the session facilitator and other participants, which will facilitate a more active form of learning, with a higher degree of interaction than the previous arm.**
- *Arm 4-Experimental group 4:* Intervention using immersion 360 degrees specifically designed for this study. **Participants enrolled in this arm, by completing it, is assumed that will experience a form of learning more participatory and immersive than conventional videos, as they can interact with the content by changing the camera angle.**
- *Arm 5-Experimental group 5:* Virtual Reality intervention specifically designed for this study. **Using VR to learn procedures will encourage caregivers to learn in a fully immersive and participatory environment where they will have to interact with the virtual content, enhancing their learning experience.**
- *Arm 6-Experimental group 6:* Augmented Reality Intervention specifically designed for this study. **This intervention will increase participants' skills through active learning as they interact with real-world care situations while receiving simultaneous support from AR devices.**

In each of the experimental groups, key patient care situations will be developed and the educational solutions for each of the arms will be adapted.

The process of this phase of the study is summarized in the following **figure**.

The evaluation of the effectiveness of each of the arms will be measured, among other ways, by recording two attempts to execute the care situation to be trained in the intervention. This recording will be made at three different times: at the baseline visit (pre-intervention), after the intervention (post-intervention) and 6 months after the end of the intervention (follow-up). The control group is an exception, as there is no specific intervention and therefore the post-intervention recording is omitted. Thus, in the case of the control group, only the pre-intervention and 6 months after the intervention will be recorded.

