- *Arms with intervention at home (Arm 2 - Intervention with written materials and videos, Arm 4 - Intervention with 360° materials and Arm 6 - Intervention with augmented reality):* the intervention is carried out by the caregiver alone at home, so it is useful to hold a training session at the centre to explain to the caregiver the task to be carried out at home.
- *Arms with intervention at the centre (Arm 3 - psychoeducational intervention, Arm 5 - intervention with virtual reality):* the stipulated sessions of each arm will be carried out in the rooms provided in the centres.

Post-intervention visit

Once each arm's own intervention has been received, participants will be called to participate in a new recording of the care work in the medical centre. As in the pre-intervention, at the beginning of the recording, the caregiver's identification code must be shown. At the end, a new link and QR with the Post-intervention Caregiver's Notebook will be shared with them so that they can fill it in online through the link. This flow will be for all arms except for the control arm (Arm 1), where no recording will be carried out and no post-intervention caregiver's notebook will be completed.

Again, the videos resulting from the recordings of this session should be analysed following the available rubric.

Follow-up visit (+6 months)

After 6 months (follow-up phase), participants will be recorded making two attempts at the care they were trained in. As in the previous recordings, at the beginning of the recording, the caregiver's identification code must be shown. At the end, they will be given a new QR and link to the Caregiver's Notebook Follow-up.

Gold Standard (professional group)

In addition to the participants in the control and experimental groups, the study will also include a group of 10 healthcare professionals, who will act as the Gold Standard group. This group will be recorded performing all the care situations to be trained to have a standard measure with which to compare the performance of the caregivers, once they have received the training.

Data analysis

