Time of use will be recorded and correlation analyses will be performed to determine the size and direction of the effect on the outcomes. The difference between the measures considered above rated will be considered before and after (PRE and POST intervention (time 0) and FOLLOW UP (+6 months)) the experimental intervention sessions as outcome variables. The distribution of the data will be tested using the Kolmogorov-Smirnov test, the measures will be compared with an ANOVA test for normally distributed continuous variables, and the Kruskal-Wallis test if the distribution is not normal. Given the number of time-ordered and repeated variables per subject, they will be explored using a linear mixed effects model (LMM). Data will be stratified taking into account gender, age, recipient profile and time of use. P values <0.05 are considered to indicate statistically significant differences. Statistical analyses will be performed on R and SPSS. If the intervention is successful, the control group will be invited to receive the treatment of the experimental group on the same terms. The results of this project will be prepared for dissemination according to the contents of the "Standards for reporting qualitative research" (SRQR) guidelines for qualitative studies, the Consort checklist for randomized trials, and the CHEERS checklist for economic outcome evaluations.

Discussion sobre utilidad o lo que hacen otros estudios

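### Arm 3 is taught in shared sessions, yet no planned analysis states a session-group term; if outcomes correlate within sessions, comparisons involving Arm 3 are anti-conservative

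*Combined protocol and SAP*

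**What the plan says.** The first Intervention design section (under Methods) specifies "simple random assignment of participants to one of six arms", so the individual is the unit of randomisation. Under Phase 2, the description of Arm 3 says that "participants will learn by sharing information with the session facilitator and other participants", and it presents this exchange as what makes the arm more active than written materials and videos.

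The Intervention part of Chronological development of the project places Arms 3 and 5 at the centres: "the stipulated sessions of each arm will be carried out in the rooms provided in the centres". Arms 2, 4 and 6 are carried out by each caregiver on their own at home, after an explanatory session at the centre. Control participants are not called in at all.

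The Data analysis section takes differences between PRE, POST and follow-up as outcomes. For continuous outcomes, "the measures will be compared with an ANOVA test for normally distributed continuous variables", with Kruskal-Wallis if normality fails. Of the repeated measurements on each person it says "they will be explored using a linear mixed effects model (LMM", and it lists no random effects. The stratifying factors are the caregiver's gender and age, the profile of the person cared for, and usage time. Session group, facilitator and centre do not appear. The threshold is "P values <0.05 are considered to indicate statistically significant differences".

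**The concern.** Individual randomisation makes the arms comparable at baseline. It does not keep participants independent once they have been taught together. Caregivers in one Arm 3 session share a facilitator, a discussion and each other's contributions, and the outcome is rubric-scored performance of the trained task. Some similarity within a session is therefore plausible.

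ANOVA and Kruskal-Wallis take the 70 or so Arm 3 caregivers as independent pieces of information. A mixed model with only a participant effect handles correlation between visits of one person, not between people. If session-mates resemble each other, the Arm 3 mean is less precise than these methods report.

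The trial sets out to find the most effective educational solution. Understated uncertainty in one arm would tilt that comparison towards declaring a difference, in either direction, where Arm 3 is involved. If session membership is not recorded during the trial, it may not be recoverable afterwards.

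**Working it through.** **Inputs from the documents.** 420 participants and six arms (Abstract: "6 groups, 5 experimental groups and control, with pre-post- intervention and follow up measures"), individual randomisation, and a 0.05 threshold.

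**Assumptions.** Equal allocation, 420/6 = 70 per arm (the ratio is not stated); a two-sided test (sidedness is not stated); Arm 3 group size m = 5, 7, 10 or 14, that is 14, 10, 7 or 5 groups; ICC ρ = 0 to 0.10; equal total variance in both arms. The sample size of 420 comes with no derivation, so there is no design figure to reproduce.

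**Step 1: contrast of Arm 3 with an arm that has no session groups.** The design effect applies to Arm 3 only:

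DEFF = 1 + (m − 1)ρ

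ratio of true to assumed variance: r = (1 + DEFF)/2

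true error = 2 × [1 − Φ(1.96/√r)]

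Example with m = 10 and ρ = 0.05: DEFF = 1.45, r = 1.225, √r = 1.107, 1.96/1.107 = 1.771, true error 7.7%.

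| ICC | m = 5 | m = 7 | m = 10 | m = 14 | true SE / assumed SE |
|---|---|---|---|---|---|
| 0 | 5.0% | 5.0% | 5.0% | 5.0% | 1.00 |
| 0.01 | 5.2% | 5.3% | 5.5% | 5.8% | 1.01-1.03 |
| 0.05 | 6.2% | 6.8% | 7.7% | 8.9% | 1.05-1.15 |
| 0.10 | 7.4% | 8.6% | 10.4% | 12.7% | 1.10-1.29 |

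**Step 2: simulation check** (8,000 trials per setting, no true difference, m = 10). Rejection rates for the two-sample t test, the ANOVA contrast and the six-arm overall F test were 7.3%, 7.3% and 6.6% at ICC 0.05, and 10.9%, 10.8% and 9.1% at ICC 0.10. The formula holds for the contrasts, and the overall test is affected less. Kruskal-Wallis was not simulated; it rests on the same independence assumption.

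**Step 3: does a mixed model with a participant intercept alone solve it?** Let w be the correlation between visits of one person, with the group effect arising after baseline. For change from PRE to follow-up:

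r = 1 + (m − 1)ρ / [4(1 − w)]

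With m = 10 and ρ = 0.05 the numerator is 0.45. For w = 0.3, r = 1 + 0.45/2.8 = 1.161 and the error is 6.9%. For w = 0.5, r = 1.225 and the error is 7.7%. For w = 0.7, r = 1 + 0.45/1.2 = 1.375 and the error is 9.5%. So it does not.

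**Step 4: which group term works?** Take 70 against 70, seven Arm 3 groups of 10, and residual variance 0.5 per visit, so the variance of one person's change is 1.

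- Group intercept constant over time: it subtracts out of the change. SE = √(1/70 + 1/70) = 0.169 whatever its variance.
- Group effect after baseline only, variance g: SE = √(2/70 + g/7). This gives 0.189 at g = 0.05, 0.207 at g = 0.10 and 0.267 at g = 0.30.

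Only the second form widens the interval for the change contrast.

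**The case against.** **Certainty.** A reader might infer that the Arm 3 standard errors are too small and that its error rate exceeds 5%, as established facts. The documents do not support that. Both statements need a positive ICC, and neither ICC nor group size is given; the text defers delivery details to later sections that are not in the supplied document. At ICC 0 there is no error, and at 0.01 the excess is below one percentage point. This stands, so the finding is conditional.

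**The mixed model.** A reader might also infer that every planned analysis treats Arm 3 participants as independent. That is true of ANOVA and Kruskal-Wallis. For the mixed model it is inference from silence: a group term is unstated, not excluded. This stands too, but the stated motive covers only repeated measures per person, and nothing commits the analyst to more.

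**Number of comparisons.** One could say that 5 of 15 pairwise comparisons are affected. The plan lists no pairwise comparisons. Control also has no POST recording, so with five arms at POST the count would be 4 of 10; 5 of 15 could apply only at follow-up.

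**Centre.** The strongest technical objection is that session group cannot be judged apart from centre. If the numbers per arm were effectively fixed within centres, an analysis ignoring centre would be conservative, with a variance ratio of roughly 1 − (centre ICC) + (m − 1)ρ/2. At an assumed centre ICC of 0.05 and m = 6, ρ = 0.01 gives 0.975 (error about 4.7%) and ρ = 0.02 gives 1.00 (5.0%). So the net direction across all sources of correlation is not settled by the documents. But the plan specifies simple randomisation, uneven participation of centres in the arms could push the other way, and larger session ICCs outweigh the offset. Centre is a separate gap. It does not make it sound to leave out session group.

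**Conclusion.** The point holds in conditional form. Shared teaching is the stated mechanism of Arm 3, no such grouping is described for Arms 1, 2, 4 and 6, and no planned analysis states a term for it. If outcomes correlate positively within session groups, and centre effects are set aside, comparisons involving Arm 3 are anti-conservative.

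The size is not fixed by the documents. It runs from negligible at ICC 0.01 to a true error of more than twice the nominal rate at ICC 0.10 with groups of 10 or more, under the assumptions of equal allocation and two-sided testing. This is a defect worth correcting before data collection because the correction is cheap and depends on data that must be captured at the time. It does not invalidate the trial, and it does not reach comparisons that leave out Arm 3, except through the overall test.

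**What to change.** 1. Record a session-group identifier and a facilitator identifier for each Arm 3 participant, and state the planned group size and number of groups.
2. Base comparisons involving Arm 3 on a partially nested mixed model in which the session-group random effect applies to Arm 3 only and only to measurements after baseline. Either of two forms will do:
   - a model of the POST or follow-up score (or the change), adjusted for PRE, with a random group intercept in Arm 3; or
   - the repeated-measures mixed model with a group-by-time (post-only) random effect in Arm 3.
3. In either form, allow arm-specific residual variance and use Satterthwaite or Kenward-Roger degrees of freedom, because there may be as few as 5 groups (70/14).
4. Do not rely on a time-constant group intercept in the repeated-measures model; it cancels from the change contrast.
5. Treat Arm 5 in the same way only if its centre sessions are in fact shared. The documents place them at the centres but do not say that participants attend together.

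The cost is the identifiers in item 1, a small change to the model, and somewhat wider intervals for Arm 3 comparisons, which reflect real uncertainty. No additional visits are needed.

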These recordings will be assessed by means of an objective checklist (rubric), which assesses the errors and learning on which the educational solutions have an impact. This task will be carried out by members of the research team.

Chronological development of the project

Screening visit:

Caregivers will be informed about the study, what their commitment is, what is needed from them and the requirements. Those who are interested and meet the inclusion and exclusion criteria (described in the section Inclusion/exclusion criteria and recruitment), will be asked to sign the consent form.

Subsequently, the centers will randomly assign participants to one of the study arms and construct the registration code for each caregiver, following the guidelines in the recruitment section (the caregiver's date of birth is required).

Start-up visit (Pre-intervention):

At this point, the carers will go to the medical centre to which they belong, where they will be recorded carrying out their simulated carer's work. The recording will be made using a device consisting of neutral glasses or a headband with a small camera to record comfortably. At the beginning of the recording, the caregiver's identification code must be shown. In the same session, at the end of the recording, the centres will explain to the participants that they must fill in a questionnaire with their data, the Pre-intervention Carer's Notebook, which can be accessed from a QR code/link that will be given to them at that moment.

Subsequently, the videos of the start-up sessions of each participant will be recorded and assessed by the research team with the help of staff from the centres following the rubric provided.

Intervention:

- *Intervention application (different sessions according to arm, arms 2 to 6 only).*

At this point, the corresponding intervention will be carried out for each participant. Depending on the arm to which he/she has been assigned, the procedure and duration of the intervention sessions will be different. The information for each intervention is explained in the following sections. It will follow the following scheme:

- *Arm 1 (Control group):* no specific intervention different from the natural one is performed so it will not be necessary to convene the participants of this group for this session.

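### The arm is assigned before the PRE recording and PRE notebook are collected, so the baseline for the difference outcomes is not a pre-randomisation measure and is open to influence by knowledge of the arm

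*Combined protocol and SAP*

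**What the plan says.** The order of events is set out in Chronological development of the project.

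- **Screening visit.** Carers are informed and checked for eligibility, and those who qualify "will be asked to sign the consent form". The next step, still under this heading, is: "Subsequently, the centers will randomly assign participants to one of the study arms and construct the registration code for each caregiver". No outcome measure is listed before it.
- **Start-up visit (Pre-intervention).** This is the next heading: "At this point, the carers will go to the medical centre to which they belong, where they will be recorded". In the same session, once the recording is over, carers are told that "they must fill in a questionnaire with their data, the Pre-intervention Carer's Notebook", which they reach by a QR code or link.
- **Intervention.** Arm-specific activity appears only under this later heading, which also says that controls need not be called in.

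Intervention design (Phase 2) identifies the pre-intervention recording as the baseline visit and specifies two recorded attempts at each time point. Data analysis then takes the measures "before and after (PRE and POST intervention (time 0) and FOLLOW UP (+6 months)) the experimental intervention sessions as outcome variables". The control arm has no post-intervention recording or notebook, so its only change is from PRE to the 6-month follow-up.

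**The concern.** Randomisation makes arms comparable, apart from chance, on anything measured before the draw. It gives no such guarantee for a measure taken after the draw if the arm could be known when the measure is taken. Here the centres make the assignment, host the PRE session and help to rate the PRE videos. The text does not say that the arm is kept from anyone until PRE is finished. The arms range from no convened session to virtual reality, so a carer or staff member who knew the arm might behave or answer differently at PRE.

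Because the outcomes are differences from PRE, an arm-related shift confined to PRE would appear in the contrast as an effect of opposite sign. Adjusting for PRE would shrink it but not remove it, since the covariate itself would have been affected by assignment. The order also means that a carer who is assigned but never attends start-up is randomised with no baseline at all.

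**Working it through.** **1. Order of steps.** Reading the headings in sequence gives: consent, assignment by the centre, PRE recording, PRE notebook, intervention. PRE precedes training but follows randomisation. No interval between assignment and start-up is stated.

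**2. Inputs.** From the documents: 420 participants and six groups (Abstract), simple random assignment (Methods, Intervention design), and P < 0.05 (Data analysis). The documents give no effect size, SD, power, correlation or dropout rate, so 420 cannot be reproduced; the timing point does not depend on it. Assumed here: equal split (420 / 6 = 70 per arm), two-sided testing, equal SDs at PRE and follow-up, a PRE-to-follow-up correlation r of 0.3 to 0.7, and a PRE shift d of 0.1 to 0.3 SD in one arm.

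**3. Bias when the shift affects PRE only and there is no true effect.**

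- Change score: 0 − d = −d, so 0.1 to 0.3 SD in size.
- PRE-adjusted contrast: 0 − r × d = −r × d, from 0.3 × 0.1 = 0.03 to 0.7 × 0.3 = 0.21 SD in size.

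A mixed model with PRE among the repeated outcomes behaves like the change score if the arm means at PRE are left free.

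**4. Bias when a fraction k of the shift persists to follow-up.**

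- Change score: kd − d = −(1 − k)d, which is zero when k = 1.
- PRE-adjusted contrast: kd − rd = (k − r)d.

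For d = 0.2 and k = 0.5, the change-score bias falls from −0.2 to −0.1 SD. The step 3 figures are therefore the largest change-score bias for each assumed d when k lies between 0 and 1.

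**5. What the step 3 bias would do to one pairwise test.** In SD units the standard errors are √(2(1 − r)) × √(2/70) for the change score and √(1 − r²) × √(2/70) for the adjusted contrast, with √(2/70) = 0.169. The rejection rate is Φ(bias/SE − 1.96) + Φ(−bias/SE − 1.96), using the size of the bias. For d = 0.2 and r = 0.5 the change-score SE is 0.169, the ratio is 0.2 / 0.169 = 1.18, and the rate is 0.219.

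| r | d | Change-score bias | False-positive rate | Adjusted bias | False-positive rate |
|---|---|---|---|---|---|
| 0.3 | 0.1 | −0.10 | 0.079 | −0.03 | 0.054 |
| 0.3 | 0.2 | −0.20 | 0.170 | −0.06 | 0.066 |
| 0.3 | 0.3 | −0.30 | 0.323 | −0.09 | 0.086 |
| 0.5 | 0.1 | −0.10 | 0.091 | −0.05 | 0.063 |
| 0.5 | 0.2 | −0.20 | 0.219 | −0.10 | 0.105 |
| 0.5 | 0.3 | −0.30 | 0.427 | −0.15 | 0.176 |
| 0.7 | 0.1 | −0.10 | 0.119 | −0.07 | 0.089 |
| 0.7 | 0.2 | −0.20 | 0.333 | −0.14 | 0.213 |
| 0.7 | 0.3 | −0.30 | 0.630 | −0.21 | 0.413 |

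With d = 0 the rate is 0.05 throughout. Measuring PRE before the draw makes d = 0 by design.

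**The case against.** The strongest reply is that the harm depends on steps the documents do not describe.

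- **Knowledge of the arm.** A reader might infer that carers and recording staff already know the arm at start-up. The text says only that the centres assign. It does not say that the same individuals run the recording, or that carers have been told, and arm-specific sessions come later. This stands: what is documented is the absence of a stated safeguard, not disclosure.
- **What could shift.** A reader might infer that baseline self-efficacy and motivation are affected. The overview names these as aims, but the notebook is described only as a questionnaire with the carers' data. The recordings are scored on an objective checklist, and knowing the arm does not teach an untrained task, so d for that measure may be small.
- **Early loss.** A reader might infer that dropout between assignment and start-up is selective by arm. The documents give no dropout figure and no interval, so that is unsupported. Nor would reordering restore outcomes: a carer who leaves on learning the arm after PRE still has no difference score.
- **Late notebooks.** No text says the PRE notebook is completed at home or after training. There is only no stated deadline.
- **Unseen material.** The process figure is not shown, and the code guidelines to which the screening step refers are not in the text available for review. They might contain a safeguard, and it cannot be determined whether the code shown on camera reveals the arm. Nothing visible suggests a different order.

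These points limit the claim to a possibility of unknown size. They do not alter the written order or the dependence of the outcomes on PRE.

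**Conclusion.** The point holds as a procedural risk. The order is explicit, PRE is the baseline for the difference outcomes, and no visible text withholds the arm until PRE is complete. PRE could therefore be influenced by knowledge of the arm. No imbalance has been shown, and the documents do not establish that anyone knows the arm at start-up.

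Under the assumed d of 0.1 to 0.3 SD and r of 0.3 to 0.7, the bias would be 0.1 to 0.3 SD for a change score and about 0.03 to 0.21 SD for a PRE-adjusted contrast. Both ranges require the shift to be present at PRE alone; any part that persists to follow-up cancels in the change score. The false-positive rates rest further on 70 per arm, equal SDs and a normal approximation. For the control arm the point concerns only the PRE to follow-up change.

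**What to change.** Reorder the steps in Chronological development of the project:

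1. **Screening visit:** eligibility, consent, a registration code that carries no arm information, and the choice of care situation made independently of arm. The last item is needed because the recording is of the situation to be trained, some centres may not take part in certain arms or situations, and recruitment templates are adjusted to the arms each centre has committed to.
2. **Start-up visit:** both PRE attempts recorded and the PRE notebook submitted on site.
3. **Only then:** the arm is drawn and disclosed.

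Carers who never attend start-up are then not randomised. Any later loss can be described by arm using an observed baseline, although their difference scores are not recovered. If a centre cannot move the draw, withholding the arm from carers and session staff until both PRE items are complete would address much of the same risk, but would still leave randomised carers without a baseline if they do not attend.

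The cost is a change to the protocol and site instructions, with no extra visit or measurement and N still 420. Arm-specific sessions could not be booked until the start-up visit ends, and carers would spend a few more minutes on site. The change protects PRE only; any response to knowing the arm at later visits would remain. It should be made before carers are assigned, since a baseline taken after assignment cannot be retaken.
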